2.1.2 The MMPI in detecting underreporting and its extension to extratest measures

A growing body of evidence indicates that underreporting on the MMPI instruments generalizes to conjointly administered self-report measures. Forbey and Lee (2011) observed that individuals who produced significantly elevated MMPI-2 K and L scale scores endorsed significantly lower mean scores on several conjointly administered self-report measures assessing various symptoms of psychopathology with roughly medium to large sized effects. Additionally, Forbey and colleagues (2013) observed that scores on internalizing self-report measures, namely the Beck Depression Inventory (Beck, Ward, Mendelson, Mock, & Erbaugh, 1961), were also significantly lower for the content-based underreporting group with medium to large effects. Indeed, individuals indicated as underreporting on the MMPI-2 and MMPI-2-RF respond in a similar manner to extratest measures of psychopathology in university, VA psychiatric inpatient, and correctional settings (Forbey & Lee, 2011; Forbey et al., 2013).

Underreporting may result in false negative findings, particularly in high-stakes assessments (Crighton, Marek, Dragon, & Ben-Porath, 2017). However, limited quantitative research has focused on identifying underreporting in suicide risk assessment, a limitation noted in the current research base (Burchett and Ben-Porath, 2019). Indeed, preliminary evidence indicates that underreporting on the MMPI-2 may have implications for suicide risk assessment. During clinic intake procedures, individuals who denied current suicide ideation/behavior on both a clinician-administered phone interview and the MMPI-2 produced higher K, S, and ODep scores than those who responded affirmatively to only MMPI-2 questions or both the interview and MMPI-2 items (Glassmire, Stolberg, Greene, & Bongar, 2001). However, no research has extended this research to Veterans outside of the VA setting or examined whether the MMPI-2-RF-EX possesses similar clinical utility of previous iterations of the MMPI to accurately identify Veterans who underreport current suicide risk.

Divergent findings regarding differences in SUI scores between those classified as underreporting and those producing scores within normal limits on content-based validity scale scores support the further clinical need for examining the impact of MMPI-indexed underreporting on suicide-related criterion, including those embedded into the MMPI. While no significant mean differences in MMPI-2-RF SUI scores between these two groups have been observed (Crighton et al., 2017), including in Veteran samples (Forbey et al., 2013; Khazem et al., In Press), significant differences with small-sized effects have also been observed in other samples (Brown & Sellbom, 2020; Khazem et al., In Preparation). Further, as these studies were not aimed at identifying patterns of responding for individuals attempting to conceal suicidal ideation or intent, it is unclear how these individuals, particularly within the Veteran population, would respond to SUI items - and extratest measures of suicide risk and psychopathology. Research employing a simulated groups design in Veteran-serving clinics unaffiliated with VA is well-suited to address these limitations and expand upon previous findings.

MMPI-based research involving simulation designs have indicated the need for including indicators of underreporting when administering extratest self-report measures. Such research designs allow examination of the construct validity of the MMPI across response-style groups while maintaining experimental control over study conditions (Burchett & Ben-Porath, 2019; Dhillon, Bagby, Kushner, & Burchett, 2016). Sellbom and Bagby (2008) examined the impact of simulated underreporting on MMPI-2-RF substantive scales in undergraduate students and individuals with schizophrenia and observed that K-r and L-r added incrementally to each other in predicting underreporting in both groups, with greater effects in those diagnosed with schizophrenia. These findings were replicated in undergraduate students (Creighton et al., 2017). Other research utilizing simulation designs have noted differences in extratest measures of trait negative affectivity (Dhillon, Bagby, Kushner, & Burchett, 2016). Despite the need for research assessing whether underreporting negatively impacts the sensitivity of suicide risk assessment through simulation research designs (Burchett & Ben-Porath, 2019; Rogers, 2018), such research has not been conducted. **This research is particularly timely for populations at heightened risk of suicide - including Veterans. The proposed study addresses this absence in the research base by employing a simulation design centered on explicit underreporting of suicide risk to identify how Veterans respond to SUI and other MMPI-2-RF-EX scales when intending to conceal suicidal ideation or intent.**

Additionally, this study design affords the additional advantage of comparing SUI scores and scores of extratest measures of suicide risk between those attempting to underreport suicide risk and those testing under standard instructions.

2.3 Anticipated Results and Potential Pitfalls It is anticipated that this research will advance the detection and treatment of suicide risk among military veterans who seek clinical services outside the Veterans Affairs setting. More specifically, based on the aforementioned findings regarding the MMPI, we anticipate that the MMPI-2-RF-EX will demonstrate clinical utility in detecting simulated underreporting of suicide risk among individuals with current distress or suicidal ideation.

Participants could develop mild to moderate emotional discomfort or frustration associated with completing questionnaires or answering interview questions assessing thoughts about suicide. This potential risk is expected to be comparable to the discomfort experienced when talking with a friend or acquaintance about these same topics. If discomfort is experienced, it is not expected to be severe or to last for more than a few minutes. Participants' *confidentiality could be breached* if their identifiers are inadvertently released or accessed by a third party. This risk is expected to be low because the data are not stored or analyzed in ways that are likely to reveal a subject's identity. Breach of confidentiality could also occur if an external party or individual hacks into the Zoom interface during a participant's session. Safeguards will be implemented to mitigate this risk, including using password-protected Zoom sessions.

2.3. Benefits of the Proposed Research Results of this proposed research will have implications for future suicide risk assessment and suicide prevention efforts in Veterans through enhancing methods of identifying and responding to those at risk of suicide that would otherwise be missed by traditional methods of suicide risk assessment (i.e. false negatives).

Procedures

3.1. Research Design. A two-arm randomized controlled simulation design will be employed in this proposed research. For both components of the study, participants will be randomized using stratified blocks of 6 or 8 participants, per recommendations by Krenan et al. (1999), based on gender and suicide attempt history (no history of suicide attempts, history of one suicide attempt, or history of multiple suicide attempts).

3.2. Sample. A sample of 150 Veterans will be included in the study and randomized to study conditions (75 in the Simulation condition and 75 in the Standard condition). Results of a priori power analyses conducted using G*Power software (Faul et al., 2007) indicate that a total sample of 150 will result in a highly-powered study ($\beta = .98\text{--}.99$) to detect medium-sized effects in all regression-based analyses. Therefore, although we anticipate low attrition from this study, the proposed sample size is sufficiently powered for the proposed analyses. Additionally, this sample size accounts for a roughly 15% rate of Non-Content-Based Invalid Responding observed in other simulation-based MMPI research (Crighton et al., 2017).

Online recruitment methods for the study are include web-based survey and research recruitment systems (e.g., SurveyMonkey), listservs and forums, and social media sites (e.g., Facebook, Twitter, Reddit). Additionally, we are requesting use of ResearchMatch (RM), which is an NIH sponsored national registry for research volunteers. ResearchMatch (RM) and OSU have had a fully executed agreement since August 2009. The IRB of record for ResearchMatch is Vanderbilt University. The Principal Investigator will be authorized to recruit study participants.

We will enroll any prospective Veteran meeting inclusion criteria (18 years of age or older, US military veteran, death or suicidal ideation/suicide attempt within the past month) in the proposed study. Exclusion criteria include: non-Veteran status, acute intoxication or active psychosis precluding

provision of informed consent, an inability to communicate and comprehend English, residence outside the United States, and lack of past-month death/suicide ideation or attempt. Participants recruited through web-based survey and research and recruitment systems will provide consent for study personnel to initiate contact through email or phone call, while those recruited through other online methods (e.g., listservs, forums) will be provided contact information for study personnel in order to inquire about the study or schedule participation.

3.3 Measurement/Instrumentation. The following self-report measures will be administered through Qualtrics online survey software during baseline procedures as part of the proposed research:

MMPI-2-RF-EX. The MMPI-2-RF-EX The MMPI-2-RF-EX was developed for research purposes in order to develop the MMPI-3 (Ben-Porath & Tellegen, 2020), which is comprised of a subset of MMPI-2-RF-EX items. While completing the MMPI-2-RF-EX, all participants will be monitored remotely by study personnel using a web camera and OSU CarmenZoom to ensure test integrity, as required by the study funding agency. While completing the MMPI-2-RF-EX, participants will simultaneously select the MMPI-2-RF-EX item numbers corresponding to those they believe are assessing current suicide risk through a separate internet browser or tab opened to a link in Qualtrics provided by study personnel.

Suicide Cognitions Scale (SCS; Bryan et al. 2014). The SCS is an 18-item survey measuring suicide-related thoughts and beliefs, unclouding hopelessness, perceived burdensomeness, entrapment, and unbearability. Respondents rate their agreement with each statement on a 5-point Likert scale. Item responses are summed, with higher scores indicating more severe suicide risk.

Beck Scale for Suicide Ideation-Current (BSS; Beck & Steer, 1991). The BSS is a 21-item measure of past-week suicide ideation and desire for death. Responses to items are scored on a 3-point Likert scale (range of 0- 2), with higher scores indicating greater suicide risk.

Short Grit Scale (Duckworth & Quinn, 2009). The Short Grit Scale is being administered to examine whether those randomized to the Simulated Underreporting condition endorse lower mean scores when compared to those randomized to the Standard Instructions condition (e.g., whether simulated underreporting of suicide risk extends to extratest measures that do not explicitly measure suicide risk).

PTSD Checklist for DSM-5 (PCL-5; Weathers et al., 2013). The PCL-5 is a self-report measure assessing the severity of 20 PTSD symptoms. Respondents rate the severity of each symptom during the past week on a 5-point Likert Scale ranging from 0 (*Not at all*) to 4 (*Extremely*). Similar to the Short Grit Scale, the PCL-5 is being administered to examine whether Veterans in the Simulated Underreporting groups endorse lower mean scores than those in randomized to the Standard instructions group.

Posttest Inquiry. All participants will be administered the MMPI-2-RF-EX Posttest Inquiry (PTI) that has been administered in previous MMPI simulation studies (Creighton et al., 2017), based on recommendations by Rogers (2008). The PTI assesses participants' compliance with condition-specific instructions for completing the MMPI and was adapted for the proposed research. Responses to three questions from this survey ("What instructions did you receive for completing the research study"; "I tried to answer the questions so I would look like I am not suicidal?"; "I tried to appear as suicidal as I could when I took the test") will be examined to assess compliance with instructions. Simulators answering "To fake not having thoughts of suicide" to the first question will be classified as Simulation- Compliant. Alternatively, Simulators answering at least "most of the time" to the second item and "not at all" to the third item will be classified as Simulation-Noncompliant and excluded from analyses. Veterans in the Standard Instructions condition who comply with instructions (e.g., do not produce profiles indicative of content-based invalid responding) are classified as Standard - Compliant while those who do not will be classified as Standard - Noncompliant and excluded from analyses.

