**Assessing the Utility of MMPI-2-RF-EX in Detecting Simulated Underreporting of
Current Suicide Risk in Military Veterans**

NCT: 2020B0414

Study Protocol and Statistical Analysis Plan

Approved 2/25/2021

Assessing the Utility of MMPI-2-RF-EX in Detecting Simulated Underreporting of Current Suicide Risk in Military Veterans

1. Objectives

The aims of the current project are: 1) to examine the incremental predictive utility of the MMPI-2-RF-EX validity scales (L and K) in detecting simulated underreporting of suicide risk on the SUI scale and extratest measures of suicide risk (Suicide Cognitions Sale, Beck Scale for Suicide Ideation – Current) and 2) compare the use and preliminary effectiveness of a self-administered version of the Crisis Response Plan (CRP) in decreasing suicidal/death ideation and distress and increasing positive affect when compared to a clinician-administered version of the protocol in a sample of 150 military Veterans experiencing current death or suicidal ideation. Hypotheses include: **(H1)** Veterans following instructions to underreport suicide risk (Simulated Underreporting) would endorse significantly higher MMPI-2-RF-EX L and K scale scores than those administered the MMPI-2-RF-EX and extra test measures under standard conditions (Standard Instructions); **(H2)** Veterans randomized to the Simulated Underreporting group will produce significantly lower scores on MMPI-2-RF-EX (SUI) and extra test self-report measures of suicide risk (Suicide Cognitions Scale, Beck Scale for Suicide Ideation – Current) than the Standard Instructions group; **(H3)** lastly, L and K would contribute incremental predictive validity over one another in differentiating between veterans in the Standard Instructions and Simulated Underreporting group. Exploratory analyses will be conducted to examine whether those randomized to Simulated Underreporting endorse lower mean scores on extratest measures that do not assess suicide risk.

2. Background and Rationale

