3.8.1. MMPI-2-RF-EX scale scores and extra test measures. Following methods employed in prior simulation research designs (Sellbom & Bagby, 2008), mean differences in scores on MMPI-2-RF-EX L, K, and SUI scales, and extratest measures of suicide risk (BSS), suicide-related cognition intensity (SCS), and measures of other psychopathology (PCL-5, Short Grit Scale) will be compared between Standard and Simulated Underreporting groups through a one-way Multivariate Analysis of Variance (MANOVA). Additionally, two stepwise hierarchical regression analyses will be conducted in order to assess the incremental predictive utility of MMPI-2-RF-EX K and L scales in identifying individuals classified in the Simulated Underreporting condition, consistent with previous literature (Sellbom & Bagby, 2008). The first model will contain the K scale in the first step and the L scale in the second step. The analysis will be repeated with the K and L scales entered into the opposite step.

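### H1 and H2 are tested only by one seven-outcome MANOVA that cannot decide either, and the power statement in section 3.2 covers only the regressions for H3

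*Combined protocol and SAP*

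**What the plan says.** Section 1 (Objectives) states H1 as a direction on two scales: simulators "would endorse significantly higher MMPI-2-RF-EX L and K scale scores than those administered" under standard instructions. H2 is a direction on three: simulators "will produce significantly lower scores on MMPI-2-RF-EX (SUI) and extra test self-report measures of suicide risk", namely the SCS and BSS. Measures that do not assess suicide risk are set apart: "Exploratory analyses will be conducted to examine whether those randomized to Simulated Underreporting endorse lower mean scores on extratest measures" of that kind. Section 3.3 gives that role to the Short Grit Scale ("whether simulated underreporting of suicide risk extends to extratest measures that do not explicitly measure suicide risk") and to the PCL-5 ("Similar to the Short Grit Scale, the PCL-5 is being administered to examine whether Veterans in the Simulated Underreporting groups" score lower).

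Section 3.8.1 then places L, K, SUI, BSS and SCS in one analysis with these two: "measures of other psychopathology (PCL-5, Short Grit Scale) will be compared between Standard and Simulated Underreporting groups through a one-way" MANOVA. It describes this as following earlier simulation studies. It writes out no scale-level test, alpha, direction, multiplicity rule, or rule linking the MANOVA to H1 or H2. The only other analyses are two hierarchical regressions with K and L entered in opposite orders, which serve H3.

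Section 3.2 gives power of .98–.99 (printed as beta) for N=150 "to detect medium-sized effects in all regression-based analyses", and from this draws the general conclusion that "the proposed sample size is sufficiently powered for the proposed analyses".

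**The concern.** A two-group MANOVA tests a single null: no difference on any of the seven outcomes, in either direction. Rejecting it shows that something differs somewhere. It can be rejected by L and K alone with H2 false, by an exploratory scale alone with H1 and H2 both false, or by a shift in the direction opposite to the hypothesis. Run exactly as written, it cannot tell H1 from H2 or either from the exploratory question.

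If scale-level tests are added later, the rule for declaring H1 or H2 supported would be chosen with the data in hand. The power statement has a matching gap: sufficiency for H1 and H2 cannot be judged until the tests that decide them are named.

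**Working it through.** **Inputs.** From section 3.2: N=150, 75 per arm; about 15% lost to invalid responding, so 150 × .85 = 127.5, taken as 128 (64 per arm); a medium effect, with no number given. Assumed, because the documents do not state them: alpha .05, f² = .15 for regression, d = 0.5 for a two-group mean difference, and equal correlation r = 0, .3 or .5 among the seven outcomes.

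**1. The plan's own figure.** Noncentral F for a linear regression with two predictors (K and L), λ = f²N, df = 2 and N − 3.
- N=150: λ = .15 × 150 = 22.5, power .992.
- N=128: λ = .15 × 128 = 19.2, power .979.
- One-df increment: .997 and .992.

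So .98–.99 reproduces for the K/L regressions, that is, for H3.

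**2. What a significant MANOVA means.** With two groups it is Hotelling's T²: F with 7 and N − 8 df and λ = (N/4)D². With equal correlation r, D² = [Σd² − r(Σd)²/(1 + 6r)]/(1 − r).

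*Only L and K differ, d=0.5; H2 false.* Σd² = .50 and (Σd)² = 1. For r = .3, D² = (.50 − .3/2.8)/.7 = .561.

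*Only the PCL-5 differs, d=0.5; H1 and H2 both false.* Σd² = (Σd)² = .25. For r = .3, D² = (.25 − .075/2.8)/.7 = .319.

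| True difference | r | D² | P(significant), N=150 | N=128 |
|---|---|---|---|---|
| L and K only | 0 | .500 | .892 | .824 |
| | .3 | .561 | .928 | .872 |
| | .5 | .750 | .982 | .958 |
| PCL-5 only | 0 | .250 | .556 | .475 |
| | .3 | .319 | .683 | .595 |
| | .5 | .438 | .839 | .760 |

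Shifting L and K by 0.5 SD in the wrong direction leaves D² unchanged, so the first three rows also apply to a result opposite to H1.

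**3. Power for tests that would decide H1 and H2.** Two-sided t test, noncentrality d√(N/4). The Holm and all-scales rows assume that all five H1/H2 scales truly differ by d=0.5; ranges are over r = 0 to .5, by simulation.

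| Rule, d=0.5 | N=150 | N=128 |
|---|---|---|
| One scale, unadjusted .05 | .86 | .80 |
| One scale, Holm over five | .78–.80 | .69–.70 |
| H1: both L and K at .05 | .74–.77 | .64–.69 |
| H2: SUI, BSS and SCS all at .05 | .64–.71 | .51–.61 |

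The r = 0 ends can be checked by hand: .86² = .74 and .86³ = .64. The regression value f² = .15 corresponds to d = 2√.15 = .775; at that effect every rule in the table gives .97 or more. Power for H1 and H2 therefore depends on the effect and the rule, and section 3.2 gives neither.

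**The case against.** The strongest reply is that follow-up tests are implied: section 3.8.1 speaks of comparing mean differences on each listed scale and follows earlier simulation studies. That may be the intention, and the documents do not exclude it. They also do not say which tests, at what level, or how several results combine into a verdict on H1 or H2. What stands is that the rule is not written, not that none was ever planned.

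A second reply is that the PCL-5-only case is contrived, since simulators are told to hide suicidal thoughts. This has force. The medium-to-large effects on collateral measures cited in section 2.1.2 come from people identified as underreporting, so they do not illustrate H1 being false. That row shows what the test permits, not what is likely. The split with L and K different but H2 false has somewhat better support: section 2.1.2 reports SUI differences as absent or small, though in studies not aimed at concealment.

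Third, non-directionality is not a fault in itself; the tests proposed below are also two-sided. The fault is that the omnibus result is not tied to a scale or its direction.

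A reader might also infer a familywise error near 1 − .95⁵ = .23 from five unadjusted tests. That is the chance of any one false scale (independent tests), which is not what H1 and H2 claim if each needs all its scales. On that reading no adjustment among a hypothesis's own scales is needed.

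**Conclusion.** The concern holds in this form: the one test written down for H1 and H2 cannot decide either, and the sufficiency conclusion in section 3.2 is unsupported for them. The structural point follows from the text and needs no assumed effect size. Its illustration (.89–.98 with H2 false; .56–.84 with both hypotheses false; N=150) rests on assumed alpha .05, d=0.5 and equal correlations of 0 to .5.

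Two stronger readings are tempting and are not supported. One is that .98–.99 is wrong: it reproduces for the regressions under conventional inputs. The other is that 150 Veterans are too few: one scale at d=0.5 has .86 power unadjusted (.80 at N=128), and at d=.775 every rule examined gives at least .97. The documents do not fix the effect for H1 and H2, so neither adequacy nor inadequacy is shown.

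This should be corrected before analysis. It does not call the design into question.

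**What to change.** 1. **Section 3.8.1, exploratory scales.** Take the PCL-5 and Short Grit Scale out of the confirmatory test and report them as exploratory, in line with section 1.
2. **Section 3.8.1, H1 and H2.** Decide H1 by tests of L and K, and H2 by tests of SUI, BSS and SCS, each two-sided at .05 with the hypothesised direction required. Declare a hypothesis supported only if all its scales are significant, as the wording that joins the scales in section 1 suggests. Each hypothesis is then falsely declared at most .025 of the time, and at least one of the two at most .05 (2 × .025). If claims on single scales are wanted instead, use Holm over the five. Write down one choice before the data are analysed. Any MANOVA stays descriptive and is neither the test nor a gate.
3. **Section 3.2.** Confine .98–.99 to the regressions and call it power. State power for the chosen H1/H2 rule, with its effect size and alpha, at the N left after the 15% allowance.

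**Cost.** Two paragraphs are rewritten; no participants or data are added. The stated power for H1 and H2 will be lower than .98–.99 at d=0.5: at N=128, about .64–.69 for H1 and .51–.61 for H2 if all scales are required, or about .69–.70 per scale under Holm. The single MANOVA p-value is given up as evidence.

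### Does Section 3.2 go too far in calling 150 participants enough for all the planned analyses?

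*Combined protocol and SAP*

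**What the plan says.** Section 3.2 plans 150 Veterans, 75 per arm, and describes a G*Power calculation giving .98 to .99 "to detect medium-sized effects in all regression-based analyses". The next sentence concludes that "the proposed sample size is sufficiently powered for the proposed analyses". On losses it adds that "this sample size accounts for a roughly 15% rate of Non-Content-Based Invalid Responding".

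Section 3.8.1 names the analyses. One MANOVA compares L, K, SUI, BSS, SCS, PCL-5 and Short Grit between arms, and serves H1 and H2. Two hierarchical regressions enter K and L in opposite orders, and serve H3. SUI is the first outcome named in H2.

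Section 2.1.2 reviews earlier SUI comparisons between people classed as underreporting and people within normal limits. It reports that "no significant mean differences in MMPI-2-RF SUI scores between these two groups have been observed", and that "significant differences with small-sized effects have also been observed in other samples". Because those studies were not about concealment, it says that "it is unclear how these individuals, particularly within the Veteran population, would respond to SUI items".

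Under Posttest Inquiry, Section 3.3 describes simulators "classified as Simulation-Noncompliant and excluded from analyses", and makes a parallel exclusion in the Standard arm. It gives no rate for either.

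**The concern.** The conclusion in Section 3.2 is wider than its premise. Power is given for regressions at a medium effect, and sufficiency is then claimed for everything, including a MANOVA with no power figure. For SUI, the only earlier evidence in the plan is null or small. If the true SUI difference were small, most trials of this size would miss it. A non-significant result read beside a claim of sufficiency could then be taken to show that concealment leaves SUI unchanged. Further exclusions beyond the 15% would reduce the analysed number again. The power figure is also labelled beta, and alpha, the effect metric and the model are not given.

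**Working it through.** **Inputs.** From Section 3.2: N = 150, 75 per arm, 15% loss (150 × 0.85 = 127.5, about 64 per arm). From Section 3.8.1: two regression predictors and seven MANOVA scales. Assumed, because the plan gives no values: two-sided alpha 0.05; medium as f² = 0.15 or d = 0.5; small as d = 0.2, with 0.2 to 0.4 shown.

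**1. The plan's own figure.** Noncentral F with noncentrality λ = f² × N.
- K and L tested together, N = 150: λ = 0.15 × 150 = 22.5 on 2 and 147 df, power 0.992.
- The same with N = 128: λ = 19.2 on 2 and 125 df, power 0.979.
- One predictor added at step 2: 0.997 and 0.992.

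The range .98 to .99 reproduces, read as 1 − beta.

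**2. The MANOVA at the same f².** With two groups this is Hotelling's T², a noncentral F on 7 and N − 8 df.
- N = 150: λ = 22.5 on 7 and 142 df, power 0.946.
- N = 128: λ = 19.2 on 7 and 120 df, power 0.897.

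**3. One scale alone.** Noncentral t with noncentrality d × √(n/2), n per arm. For d = 0.5 and n = 75 this is 0.5 × √37.5 = 3.06 on 148 df.

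| d | 75 per arm | 64 per arm |
|---|---|---|
| 0.2 | 0.229 | 0.202 |
| 0.3 | 0.446 | 0.391 |
| 0.4 | 0.682 | 0.612 |
| 0.5 | 0.860 | 0.801 |
| 0.6 | 0.955 | 0.920 |
| 0.7 | 0.989 | 0.976 |

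Power reaches 80% at d of about 0.46 with 75 per arm and 0.50 with 64. The 95% CI half-width, t × √(2/n), is 0.32 SD and 0.35 SD.

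**4. The two meanings of medium.** For two equal groups f² = d²/4. So f² = 0.15 corresponds to d = 2 × √0.15 = 0.77, and d = 0.5 corresponds to f² = 0.25/4 = 0.0625. At f² = 0.0625 the seven-scale MANOVA has power 0.56 with N = 150 and 0.47 with N = 128. The MANOVA result in step 2 therefore depends on reading medium in the regression metric, which is the one that reproduces the plan's figure.

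**5. Compliance exclusions.** Suppose a further 10%, 20% or 30% is lost from both arms after the 15%. The analysed N is 127.5 × 0.90 = 114.75, 127.5 × 0.80 = 102 and 127.5 × 0.70 = 89.25.
- One scale, d held at 0.5: power 0.76, 0.71, 0.65.
- Two-predictor regression, f² = 0.15: 0.96, 0.94, 0.91.
- Seven-scale MANOVA, f² = 0.15: 0.85, 0.80, 0.72.

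Holding d fixed assumes that the people removed respond like those who stay. Suppose instead that 0.5 is the average over all simulators and that noncompliers show no effect. Removing 10% or 20% then raises d to 0.5/0.90 = 0.556 or 0.5/0.80 = 0.625, and power becomes 0.84 or 0.88. This takes the compliance labels at their evident intent. The direction of the change is therefore not settled.

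**The case for a change.** The strongest case for a change is that SUI is central to H2, that the plan's own review offers no medium SUI effect, and that power is below 0.80 across d = 0.2 to 0.4. The medium to large effects in Section 2.1.2 concern other self-report measures. Even at d = 0.5, power for one scale is 0.86 rather than .98, and any further loss at that d takes it below 0.80.

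The arithmetic stands, and so does the observation that sufficiency for SUI is asserted rather than shown. The step to a defect does not. The small effects come from groups sorted by their validity-scale scores. Here participants have recent death or suicidal ideation or an attempt, are randomised, and in one arm are told to hide it, with a payment for avoiding detection. Section 2.1.2 itself sets the earlier studies apart on this ground. The plan does not assign d = 0.2 to this contrast, sets no 0.80 target, and claims nothing about small effects. The single-scale test is also an inferred follow-up, since Section 3.8.1 names only the MANOVA and the regressions. A missing expected effect is a gap in the justification, not evidence that the effect is small.

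**Conclusion.** No change is needed. The stated power is right on its own terms at an assumed f² = 0.15 and alpha 0.05. At that f² the sample also serves the MANOVA (0.95, or 0.90 after the 15% loss), and at d = 0.5 it serves a single scale (0.86, or 0.80). The figure of 0.23 depends on d = 0.2, which is not in the plan and is drawn from a different kind of comparison. The cost of the compliance exclusions cannot be signed without a rate and a view on how noncompliers respond.

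The residue is modest. The beta label is a clerical slip. The sufficiency sentence is best read as limited to medium effects. G*Power inputs, an expected SUI effect and an exclusion rate are details that could be written down without changing any estimate, test or analysed set. A larger sample would buy precision for small effects that the plan does not undertake to detect. Analysts can guard against misreading a null SUI result by giving the difference with its 95% CI: a half-width of 0.32 to 0.35 SD shows that a small effect has not been excluded.
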